## 20 PUBLICATION POLICY

At the conclusion of the study, an abstract reporting the results will be prepared and may be presented at a scientific meeting(s). A manuscript may also be prepared for publication in a peer-reviewed scientific journal. Co-authorship will be granted to the National PI and those site PIs from the top enrolling sites. Consistent with “Recommendations for the Conduct, Reporting, and Publication of Scholarly Work in Medical Journals”, every author should meet the following for authorship:

- Substantial contributions to the conception or design of the work; or the acquisition, analysis, or interpretation of data for the work; and
- Drafting the work or revising it critically for important intellectual content; and
- Final approval of the version to be published; and
- Agreement to be accountable for all aspects of the work in ensuring that questions related to the accuracy or integrity of any part of the work are appropriately investigated and resolved.

The study will also be registered in publicly accessible databases (e.g., ClinicalTrials.gov) per applicable regulation.

## 21 COVID -19 CONTIGENCY MEASURES

This section identifies contingency measures for the study procedures and various aspects of study management to address limitations to study site visits imposed by the COVID-19 pandemic in accordance with “FDA Guidance on Conduct of Clinical Trials of Medical Products during COVID-19 Public Health Emergency” (March 2020, updated on August 30th, 2021).

### 21.1 Study Procedures During COVID-19

- The implementation of contingency measures should be consistent with the protocol to the extent possible, and sponsor and clinical investigators should document the reason for any contingency measures implemented.
- Informed consent and Screening: The ICF may be sent to prospective subjects for review and discussed remotely via phone contact or virtual visit but it must be signed and dated during on-site visit prior to and on the same day as the protocol-required screening assessments to confirm initial eligibility and obtain baseline values. In the event that new information requires a subject be re-consented, the updated ICF may be sent to the subject electronically or via mail for review and discussed remotely via phone contact or virtual visit. The consent form can be signed, scanned and returned electronically to the site, returned by mail using a

prepaid envelope provided by the site, or returned in person. COVID-19 screening procedures that may be mandated by the clinical sites do not need to be entered into EDC. If a potential subject tests positive for COVID-19, the subject is considered screen failure.

- Follow-up Visit: If COVID-19 restrictions or subject's health status prevent the subject from attending a protocol-required on-site visits, those visits can be conducted remotely. The protocol-required CT and endoscopic assessment on baseline and follow-up visits shall be conducted on-site to maintain data quality and integrity for the primary and key secondary efficacy endpoints. If a subject completes the follow up visits out of window because of COVID-19, this will be reported as a protocol deviation with COVID-19 as a reason. The data from these late visits can be leveraged based on scientifically based rationale and clinical judgement.
- CT and endoscopy assessment: If the CT or endoscopy assessment cannot be completed within the visit window, they can either be completed within reasonable (< 30 days) from the visit window or be left as not done. These will be reported as a protocol deviation with COVID-19 as a reason.
- SNOT-22, RSI and CRS side-specific symptom questionnaire: The study staff can mail the paper questionnaires to the subject's home for completion during a virtual study visit. The completed and initialed questionnaires can be returned to the site in person or using envelopes provided by the study site. The visit type will be recorded in the EDC.
- Reporting of any AEs, device deficiencies and change in concomitant medications: These can be completed during virtual visit and documented in the EDC.

## 21.2 Contingency Measures for Study Management

- SIV training: The required training can be completed through web-based self-training or in person through video conferencing. The training must be documented.
- Data monitoring: In the event an in-person study site visit is not permissible, CRAs will perform remote monitoring. Remote monitoring will include remote source data verification and collection of essential documents. Remote performance of source data verification will require the site research coordinator to redact, scan and send certified copies of source documents to a secure, cloud-based portal or through email. Redacted copies should be kept in the investigator's site master file with records of their communication to the monitor. Uploaded source documents will be accessed by site monitors for source verification with entries in EDC. Issues identified and their resolution will be tracked through annotations made in EDC. Discrepancies between source and EDC will be managed and documented through the EDC query resolution process. Once source data verification is complete, the CRA will securely destroy any copy made locally and provide a certificate of destruction to the trial site.

- EMR system: If local study site policies allow access to the site EMR system, collection of electronic medical records may be completed using the same process. If local study site policies allow access to the site EMR system, the CRA should be provided with secure, read-only access, including all modules relevant for review. This access should be restricted to the records of only those patients who participate in the trial. A list of the monitors to whom remote access has been granted should be maintained. In order to prevent unauthorized access, access rights should be revoked once remote SDV tasks have been completed for the trial. The EMR system should have an audit trail and be able to log information on who accessed data and when. Remote access to the EMR should only be possible using a two-factor authentication. It should not be possible to make local copies of trial participants' health records. Users should be aware of the automatic creation of temporary files on their computer when reviewing trial participant data and should securely delete such files immediately after each source data verification session.
- Situations where CRAs were unable to access or had delayed monitoring of a clinical site shall be documented, including whether identification of deviations or GCP non-compliance was delayed due to postponed monitoring findings and action items resulting from remote monitoring can be discussed with PI and site coordinator via teleconference. Monitoring activities shall be documented per normal procedure.
- Reporting of protocol deviations: When a deviation is the result of a COVID-19 limitation, the deviation report shall include the specific limitation imposed by COVID-19 leading to the inability to comply with the protocol.

## APPENDIX I: LIST OF CORTICOSTEROID MEDICATIONS

Trade Name (alphabetical order)	Generic Name	Route of Administration
Budesonide Pulmicort Respules	Budesonide	Nasal (e.g., irrigations, rinses)
Decadron Dexasone	Dexamethasone	Intramuscular Oral
Depo Medrol Medrol Medrol Dosepak Methylprednisolone	Methylprednisolone Methylprednisolone Acetate	Oral Parenteral routes (e.g., intra-articular, intra-cervical)
Flovent Flonase Xhance	Fluticasone Propionate Fluticasone Propionate w/Salmeterol	Nasal irrigations Intranasal sprays
Kenalog	Triamcinolone Triamcinolone Acetonide	Intramuscular Subcutaneous Submucosal
Nasonex	Mometasone furoate	Nasal irrigations Intranasal sprays
Deltasone Prednicot Sterapred	Prednisone	Intramuscular Oral

2 REVISION HISTORY

Revision	Revision Date	Summary of Changes
1.0	29-NOV-2021	Initial release
2.0	20-MAY-2022	
• Replaced all instances of FSO maximum diameter with FSO minimum diameter• Tables 1 and 2 reorganized based on type of analysis (primary and key secondary; secondary and exploratory) instead of timepoint (Day 45; Day 90 and 180)• Sec. 4.5 specified major procedural protocol deviations and updated analysis populations for primary and secondary analyses• Sec. 6.1 and 9.8 specified the type of data collected and analyses to be performed for endpoints and economic measures• Sec. 9.2 updated the definition of primary efficacy endpoint and implant success rate per updated study protocol (CP-00030 Rev 5.0)• Sec. 9.4 replaced key secondary endpoint of polypoid edema in the frontal recess/FSO with FSO minimum diameter at Day 45 on CT by an independent, blinded reviewer• Added CP-00030, CP-00038, and R 28020 to references• Made minor clarifications, edits, and editorial changes throughout

3 LIST OF ABBREVIATIONS

Abbreviation	Expansion
ADE	adverse device effect
AE	adverse event
BSD	balloon sinus dilation
CIP	clinical investigational plan
CRF	case report form
CRS	chronic rhinosinusitis
CSR	clinical study report
CT	computed tomography
EDC	electronic data capture
e.g.	‘exempli gratia’ in Latin, meaning ‘for example’
ESS	endoscopic sinus surgery
et al	‘et alia’ in Latin, meaning ‘and others’
FDA	Food and Drug Administration
FSO	frontal sinus ostium/ostia
FSOT	frontal sinus outflow tract
GCP	good clinical practice
ICH	International Council on Harmonization
i.e.	‘id est’ in Latin, meaning ‘that is’
INCS	intranasal corticosteroids
ITT	Intent-to-treat
MedDRA	Medical Dictionary for Regulatory Activities
OS	frontal sinus outflow narrowest diameter
PTE	per-treatment evaluable
RSI	Rhinosinusitis Symptom Inventory
SADE	serious adverse device effect

SAE	serious adverse event
SAP	statistical analysis plan
SNOT	Sino-Nasal Outcome Test
SOP	standard operating procedure
UADE	unanticipated adverse device effect
USADE	unanticipated serious adverse device effect
WHO	World Health Organization

4 INTRODUCTION

This document outlines the statistical analysis plan (SAP) for the EXPAND Study conducted by Intersect ENT under protocol P500-1220 entitled “The EXPAND Study: A Clinical Evaluation of PROPEL® Contour Placement Following In-office Frontal Sinus Balloon Dilation”. Preparation of this SAP was based on the EXPAND study protocol version 5.0 dated 20 May 2022. The SAP specifies the data listings, tabular summaries, and analyses to be performed.

4.1 Study Objective

The objective of the EXPAND study is to evaluate the efficacy of PROPEL Contour placement in the frontal sinus ostium (FSO) following in-office frontal sinus balloon dilation (SBD) in patients with chronic rhinosinusitis (CRS).

4.2 Study Design

This is a post-market, randomized, intra-patient controlled, blinded, multicenter trial enrolling up to 80 randomized subjects from up to 20 US sites. Study subjects will be randomized following a successful in-office bilateral frontal BSD to receive 1 PROPEL Contour on 1 FSO side (treatment), and nothing on the contralateral side (the control treatment).

4.3 Study Visits and Assessments

Subjects are expected to return for 4 follow-up visits at Day 21, 45, 90 and 180 (end of study). Each follow-up visit includes endoscopic evaluation with video recording, and computed tomography (CT) scan will be performed at Day 45 and 180 (see **Appendix A**).

4.4 Sample Size and Power

The sample size was calculated based on the mean difference in the cross-sectional area of the FSO by CT at Day 30 between the treatment and control sides from subjects in the PROGRESS study who underwent bilateral frontal BSD followed by unilateral placement of PROPEL Contour with the following assumptions:

- Expected mean difference of 9 mm² between the treatment and control sides
- A standard deviation (SD) of 18 mm² for side-to-side difference
- Target power of 95%
- Type I error rate of $\alpha = 0.05$, 2-sided

Internal, unpublished data suggest that SD = 18 is a reasonable assumption and that an achievable difference in mean cross-sectional areas of the FSO may be greater than 9 mm². The 9 mm² is deemed to be a clinically important difference to detect. Based on standard formulas for a t-test, a sample size of 56 subjects provides at least 95% power to detect a difference of 9 mm² in mean FSO cross-sectional area between treatment side and control side. Assuming up to 20% of subjects

with non-evaluable data on one or both sides, as it was reported in PROGRESS study report (R 28020), an additional 24 subjects will be enrolled for a total of 80 randomized subjects. Sample size calculations were carried out in PASS 14 (PASS 2015).

4.5 Analysis Populations

The analysis of the primary and key secondary endpoints at Day 45 will be conducted on the intent-to-treat (ITT) population. The secondary endpoint analyses will be performed on the ITT and per-treatment evaluable (PTE) populations through Day 180. The exploratory endpoint analysis will be performed on the PTE population. The safety will be evaluated on the safety population. All analysis populations are defined below:

- *ITT Population.* All randomized subjects and sinuses in whom SBD followed by placement of PROPEL Contour in the target sinus was attempted. An attempt occurs when the physician introduces the delivery system into the subject's nostril with the intent of implant placement. Subjects' sinuses are analyzed in the treatment group to which they are randomized. This is the main analysis population for the primary and key secondary efficacy endpoints.
- *PTE Population.* All randomized subjects who have received PROPEL Contour in the target sinus, who have no major procedural protocol deviations (e.g., underwent study-related prior to informed consent, received treatment other than assigned by randomization), and for whom follow-up data are available. This population will be used for the secondary and exploratory endpoints.
- *Safety Population.* All subjects and sinuses exposed to PROPEL Contour. This population will be used for all summaries of AEs. Any subjects enrolled in the study who are not exposed to PROPEL Contour will be summarized separately.

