### **18.6 Analysis Populations**

The analysis of the primary and key secondary endpoints at Day 45 will be conducted on the intent-to-treat (ITT) population. The secondary endpoint analyses will be performed on the ITT and per-treatment evaluable (PTE) populations through Day 180 as applicable. The exploratory endpoint analysis will be performed on the PTE population. The safety will be evaluated on the safety population. All analysis populations are defined below:

- *ITT Population.* All randomized subjects and sinuses in whom SBD followed by placement of PROPEL Contour in the target sinus was attempted. An attempt occurs when the physician introduces the delivery system into the subject's nostril with the intent of implant placement. Subjects' sinuses are analyzed in the treatment group to which they are randomized. This is the main analysis population for the primary and key secondary efficacy endpoints.
- *PTE Population.* All randomized subjects who have received PROPEL Contour in the target sinus, who have no major procedural protocol deviations (e.g., underwent study-related procedures prior to informed consent, received treatment other than assigned by randomization), and for whom follow-up data are available. This population will be used for the secondary and exploratory endpoints.
- *Safety Population.* All subjects and sinuses exposed to PROPEL Contour. This population will be used for all summaries of AEs. Any subjects enrolled in the study who are not exposed to PROPEL Contour will be summarized separately.

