5.3 Secondary and Exploratory Analyses

The secondary and exploratory analyses through Day 180 (end of study) will be performed after completing primary analysis and after the database is locked, using analysis populations and endpoints detailed in

Table 2.

Table 2: Summary of Secondary and Exploratory Analyses

Endpoint	Display	ITT	PTE
Secondary			
Cross-sectional area of FSO on CT (Day 180)*	T,L	Y	-
FSOT volume on CT (Day 180)*	T,L	Y	-
FSO minimum diameter on CT (Day 180)*	T,L	Y	-
Lund-Mackay score for the frontal sinus (Day 45, 180)*	T,L	Y	-
Zinreich's score for the frontal sinus (Day 180)*	T,L	Y	-
Lund-Mackay score for the frontal sinus (Day 45, 180)**	T,L	Y	-
Need for post-operative interventions in the frontal recess/FSO (Day 21, 90, 180)**	T,L	Y	-
Adhesion/scarring grade in the frontal recess/FSO and ethmoid sinus (Day 21, 45, 90, 180)**	T,L	Y	-
Polypoid edema in the frontal recess/FSO (Day 21, 45, 90, 180)**	T,L	Y	-

CONFIDENTIAL

10 of 33

May not be reproduced outside of Intersect ENT without written permission from Document Control

Endpoint	Display	ITT	PTE
Inflammation score in the frontal recess/FSO (Day 21, 45, 90, 180)**	T,L	Y	-
Polyp grade in the ethmoid sinus (Day 21, 45, 90, 180)**	T,L	Y	-
CRS side-specific score (Day 21, 45, 90, 180)	T,L	-	Y
SNOT-22 score (Day 180)	T,L	-	Y
RSI score (Day 180)	T,L	-	Y
Implant delivery success rate	T,L	Y	-
Exploratory			
Patient satisfaction (Day 90, 180)	T,L	-	Y
Health-economic measures (Day 180)	T,L	-	Y

Abbreviations: CRS, chronic rhinosinusitis; CT, computed tomography; FSO, frontal sinus ostium; FSOT, frontal sinus outflow tract; ITT, intent to treat; L, listing; PTE, per treatment evaluable; RSI, Rhinosinusitis Symptom Inventory; SNOT, Sino-Nasal Outcome Test; T, table; Y, yes.

* By an independent, blinded reviewer.

** By clinical investigators.

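### SAP Table 2 gives no ITT analysis of the CRS side-specific score, the only patient-reported side-to-side comparison, and SAP 4.5 does not match the table

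*SAP*

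**What the plan says.** SAP 4.5 sets the general rule: "The secondary endpoint analyses will be performed on the ITT and per-treatment evaluable (PTE) populations through Day 180". Its PTE entry adds: "This population will be used for the secondary and exploratory endpoints". Neither sentence names a subset of endpoints. The ITT entry says: "This is the main analysis population for the primary and key secondary efficacy endpoints". No main population is therefore named for the remaining secondary endpoints.

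Protocol 18.6 has the same general rule with a qualifier: "The secondary endpoint analyses will be performed on the ITT and per-treatment evaluable (PTE) populations through Day 180 as applicable".

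SAP 5.3 says that the secondary and exploratory analyses are done "using analysis populations and endpoints detailed in" Table 2. That table has an ITT column and a PTE column. The rows "CRS side-specific score (Day 21, 45, 90, 180"), "SNOT-22 score (Day 180") and "RSI score (Day 180") are marked for PTE and not for ITT. Every other secondary row is marked for ITT and not for PTE.

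SAP 9.5 lists the secondary endpoints again without naming a population.

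**The concern.** The general rule and the table do not say the same thing, and neither document explains why the patient-reported scores are treated differently from the CT and endoscopic endpoints.

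The CRS side-specific questionnaire (SAP 9.2.4.3) is scored separately for left and right. SNOT-22 and RSI (SAP 9.2.4.1 and 9.2.4.2) are whole-patient scores. The side-specific score is therefore the trial's only patient-reported comparison of treatment with control.

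The ITT set in SAP 4.5 keeps every randomized subject in whom placement was attempted and analyses the sides as assigned. The PTE set removes subjects who did not receive the implant in the target sinus, who had a major procedural deviation (treatment other than that assigned is one of the examples), or who have no follow-up data. Apart from deviations that predate randomization, such as study procedures done before consent, these exclusions depend on events after randomization. At stake is whether the symptom comparison describes the assignment as randomized, or only the subjects in whom the procedure went as planned.

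**Working it through.** No design figure in the plan bears on this point. The check is a count of Table 2 followed by a comparison of the two population definitions.

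**Step 1: count the secondary rows of Table 2.**

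| Secondary rows | Number | ITT | PTE |
|---|---|---|---|
| Core-lab CT: FSO area, FSOT volume, FSO minimum diameter, Lund-Mackay, Zinreich | 5 | Y | - |
| Investigator CT: Lund-Mackay | 1 | Y | - |
| Need for post-operative intervention | 1 | Y | - |
| Endoscopy: adhesion/scarring, polypoid edema, inflammation, ethmoid polyp grade | 4 | Y | - |
| Implant delivery success | 1 | Y | - |
| Patient-reported: CRS side-specific, SNOT-22, RSI | 3 | - | Y |

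ITT only: 5 + 1 + 1 + 4 + 1 = 12. PTE only: 3. Both: 0. Total: 12 + 3 = 15.

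**Step 2: compare with SAP 4.5.** If the general rule means both sets for each endpoint, all 15 rows lack one of them. If it means that some endpoints use one set and some the other, the table can satisfy it. The PTE entry still does not fit, because it assigns PTE to the secondary endpoints without limit while 12 of 15 rows leave PTE out. On either meaning, no patient-reported score has an ITT analysis.

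**Step 3: see who separates ITT from PTE for the CRS side-specific score.** By the definitions in SAP 4.5, three groups are in ITT and not in PTE:

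- *Placement attempted, implant not received in the target sinus.* These subjects can have symptom scores; PTE drops them.
- *Major procedural deviation, including treatment otherwise than as randomized.* These subjects can have scores; PTE drops them.
- *No follow-up data.* They contribute no observed post-baseline score to either set, because SAP 6.1 plans no imputation by default.

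The real difference therefore comes from the first two groups.

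**Step 4: size.** The documents give no PTE exclusion rate. Purely as an assumption, suppose that all 80 randomized subjects are in ITT and that 0, 4, 8 or 16 of them (0%, 5%, 10% or 20%) fall outside PTE. The PTE set is then 80, 76, 72 or 64. This shows how the set shrinks. It says nothing about the direction or size of any shift in the mean score, which cannot be derived.

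**The case against.** The strongest defence is that SAP 4.5 is a general statement and SAP 5.3 hands the detail to Table 2. Read with the qualifier in protocol 18.6, on which the SAP is based, the general rule means that both sets are used among the secondary endpoints and that the table says which applies where. This is a fair reading, and it reduces the mismatch to loose wording in 4.5. It does not supply an ITT analysis of the side-specific score or a reason for leaving it out.

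Several stronger inferences are tempting, and the documents do not support them:

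- *That 4.5 demands both populations in all 15 rows.* Receiving the implant is a condition of PTE, and implant delivery success (SAP 9.2.5) is correct placement on the intended side. In PTE that rate would be close to 100% by construction, so a blanket rule makes no sense for that row.
- *That Table 1 is wrong to omit PTE for the primary endpoint.* SAP 4.5 assigns the primary and key secondary endpoints to ITT, and Table 1 does the same. No PTE analysis of the primary is promised or required.
- *That the two readings give different results.* This is not shown. ITT already requires an attempted placement, and a second attempt that succeeds counts as success. An excluded subject also loses both sides together, so no imbalance in numbers between sides arises.
- *That the population can be picked after seeing the data.* The secondary analyses do follow the unblinded Day 45 analysis, and major deviations are defined only by examples. But Table 2 names one population per endpoint in advance, and SAP 6.1 requires analyses designed after database lock to be identified as post hoc.
- *That all three scores lose a randomized comparison.* SNOT-22 and RSI have no control side. Only the CRS side-specific score is affected in that way.

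It is also true that subjects know which side was treated (protocol 19.3), which limits a self-rated side comparison under either population.

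**Conclusion.** The point holds at low severity, as a cheap improvement. SAP 4.5 and Table 2 are not aligned. The CRS side-specific score has no ITT analysis, and its PTE analysis excludes failed placements and subjects treated otherwise than as randomized, without a stated reason.

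The severity is low because the primary and all five key secondary endpoints are unambiguously ITT. The affected scores are outside the Holm family in SAP 9.4.1, which calls the other secondary endpoints exploratory or explanatory.

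The conclusion rests on the definitions in SAP 4.5 and the column marks in Table 2. It does not assume that any particular number of subjects will fall outside PTE. If every attempted placement succeeds and no major deviation occurs, the observed side-specific scores will be the same in both sets.

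**What to change.** 1. In Table 2, mark ITT as the main analysis for the CRS side-specific score, and do the same for SNOT-22 and RSI for consistency. Keep the existing PTE mark on these three rows as supportive.
2. In SAP 4.5, reword the general sentence and the PTE entry to say that populations for secondary endpoints are endpoint-specific, as listed in Table 2.
3. Leave implant delivery success as ITT only. Leave Table 1 as it is.

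The cost is a short text edit, three extra marks in Table 2 and a few extra output tables. No new data are collected, and the sample size, the primary analysis and the multiplicity procedure do not change.

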Polypoid edema in the FSO	
Polypoid edema in the frontal recess/FSO is assessed on a 4-point scale as follows:
 
 
• 0: Normal mucosa, no visible polyps/mucosal edema
 
• 1: Minimal amount of polyps/mucosal edema
 
• 2: Moderate amount of polyps/polypoid edema
 
• 3: Expanded amount of polyps/polypoid edema
 

Rhinosinusitis Symptom Inventory (RSI)	
RSI is administered using a paper (reflective) questionnaire to assess the CRS symptoms: 5 key symptoms (facial pain/pressure, facial congestion/fullness, nasal obstruction/blockage, nasal discharge or post-nasal drip, decreased sense of smell), 7 other symptoms (headache, halitosis, dental pain, cough, ear symptoms, fevers, and fatigue) on a 6-point scale of 0 to 5, as follows:
 
 
• 0: Absent
 
• 1: Very mild
 
• 2: Mild
 
• 3: Moderate
 
• 4: Severe
 
• 5: Very severe
 
 
The individual symptom scores were used to calculate 4 domain scores as follows:
 
 
• Nasal: sum of scores for nasal obstruction, rhinorrhea, sense of smell
 
• Facial: sum of scores for facial pain/pressure, facial congestion/fullness, and headache
 
• Oropharyngeal: sum of scores for halitosis, dental pain, cough, and ear symptoms
 
• Systemic: sum of scores for fevers, and fatigue
 
 
In addition, the RSI catalogs medication use (topical nasal corticosteroids, prescription antihistamines, and oral antibiotics), physician visits, and workdays missed due to CRS.

Safety population	Consists of all subjects and sinuses exposed to PROPEL Contour Sinus Implant. This population will be used for all summaries of adverse events. Any subjects enrolled in the study who are not exposed to the PROPEL Contour Sinus Implant will be summarized separately.
Serious adverse device effect (SADE)	An adverse device effect that has resulted in any of the consequences characteristic of a serious adverse event. If the nature, incidence, severity or outcome of a SADE has been identified in the device's risk analysis report, it is considered an anticipated SADE (or ASADE)

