9.7 Safety Measures

All descriptive summaries for the safety measures will be presented for the safety population analysis.

Adverse events will be coded using the Medical Dictionary for Regulatory Activities (MedDRA). Where possible, and if applicable, AE will be localized to a sinus type and side. If a subject reports the same AE more than once or experiences the same AE on multiple occasions, the maximum severity grade and relationship to the study implant, accessory devices, study implant procedure, and/or dilation procedure will be presented in subject/AE level summaries.

The incidence and percentages of subjects with an AE and serious adverse events (SAE) through Day 180, including adverse device effects, UADEs, and USADEs, will be presented by MedDRA system organ class (SOC) and preferred term (PT). In addition to the number of subjects experiencing each SOC/PT AE, the number of events will also be reported by SOC and PT. Complete subject listings of all AEs will be provided. For each AE, the following will be specified:

- Start and stop dates, and event onset (study day)
- The affected side (right or left) if available
- Seriousness
- Severity
- Strength of relationship
- Action taken
- Outcome

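### Control-side adverse events are counted only in pooled subject and event totals, and no treated-versus-control comparison of localised events is prespecified

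*SAP*

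**What the plan says.** The Safety Population in SAP 4.5 is "All subjects and sinuses exposed to PROPEL Contour. This population will be used for all summaries of AEs". Protocol 18.6 has "All subjects and sinuses exposed to PROPEL Contour", and the glossary in Protocol 4 has "Consists of all subjects and sinuses exposed to PROPEL Contour Sinus Implant". The only group set aside is defined by subject: "Any subjects enrolled in the study who are not exposed to PROPEL Contour will be summarized separately". The design is intra-patient (SAP 4.2): both frontal sinuses are dilated, one receives the implant and the other receives nothing.

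SAP 9.7 describes the tables. The first unit is the subject: "The incidence and percentages of subjects with an AE and serious adverse events (SAE) through Day 180", by MedDRA system organ class (SOC) and preferred term (PT). The second is the event: "the number of events will also be reported by SOC and PT". Side appears twice, as a collection rule ("Where possible, and if applicable, AE will be localized to a sinus type and side") and as a field in the AE listing, where available. No table by treated and control side, no side-level denominator and no between-side estimate is named. Protocol 18.5 adds only that AE incidence through Day 180 will be reported.

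**The concern.** The trial randomises sides within a subject, so its randomised safety information lies in the comparison of the two sides. A per-subject AE rate has no control group, because every implanted subject carries both a treated and a control sinus.

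This matters because the listed risks overlap. Protocol 17.1 gives epistaxis, infection, facial or nasal pain and headache for balloon dilation, and intranasal bleeding, localised infection and headache for intranasal mometasone. Both sides are dilated and one is implanted. A pooled rate for bleeding or infection therefore cannot show how much goes with dilation and how much with the implant.

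The plan relies instead on causality judgements. These are made first by investigators (Protocol 16.2.2), who are unblinded, as are subjects (Protocol 19.3). A side-by-side summary would add evidence that rests on randomisation. If it is designed only after database lock, SAP 6.1 makes it post hoc.

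**Working it through.** The plan states no figure on this point. The check is a reading of the definitions, followed by a small illustration.

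**Step 1: the population definitions in SAP 4.5.**

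| Population | Criterion | Are both sides placed by assignment? |
|---|---|---|
| ITT | placement attempted in the target sinus | Yes: a sentence assigns each subject's sinuses to their randomised group |
| PTE | implant received in the target sinus | Not stated; defined by subject |
| Safety | exposed to the implant; subjects and sinuses both named | No such sentence |

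Exposure is not defined. ITT turns on attempt and PTE on receipt, while Protocol 12.3.4 starts the treatment phase when the delivery system is introduced. A subject whose delivery fails is in ITT but may or may not be in Safety.

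**Step 2: which reading fits SAP 9.7.** The AE tables count subjects and events. Every implanted subject is an exposed subject. With all 80 planned subjects implanted, 80 subjects enter the denominators and 0 control-side events are dropped. On a strict sinus-level reading, a by-side table would have no control column. The first reading fits the tables as described; the second shows why the wording would obstruct a by-side table if one were added.

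**Step 3: what pooling hides.** For one preferred term, let a, b and c be the numbers of subjects with the event on the treated side only, the control side only, and both sides, among n subjects.

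- Planned row: (a + b + c)/n
- Side contrast: (a + c)/n − (b + c)/n = (a − b)/n

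Assume n = 80, c = 0 and 8 affected subjects with one event each. The planned tables show 8/80 = 10.0% and 8 events in every case below.

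| a | b | Side contrast | Exact McNemar p |
|---|---|---|---|
| 8 | 0 | 8/80 = +10.0 points | 2 × 0.5^8 = 0.0078 |
| 4 | 4 | 0/80 = 0 points | 1 |
| 0 | 8 | −8/80 = −10.0 points | 2 × 0.5^8 = 0.0078 |

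**Step 4: what a by-side table could show.** If all k discordant subjects fall on one side, the exact two-sided p is 2 × 0.5^k. Five give 0.0625 and six give 0.031, so at least six are needed for p < 0.05. Power of the exact McNemar test with 80 pairs was found by summing over the binomial number of discordant pairs. The event rates are assumptions, since the documents give none:

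| Treated side only | Control side only | Power |
|---|---|---|
| 5% | 1% | 11.5% |
| 10% | 5% | 13.4% |
| 10% | 2% | 43.5% |
| 15% | 5% | 43.7% |

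These values support a descriptive table with intervals, not a formal test.

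**The case against.** A reader might infer that control-side events are missing from every table and that half of the frontal sinuses have no AE summary. The documents do not support this. SAP 9.7 counts subjects and events, sets aside only unexposed subjects, and lists all AEs. The ITT definition also speaks of subjects and sinuses with attempted placement in the target sinus, yet SAP 9.3.1 takes treated minus control within ITT. The phrase is loose wording, not a rule that removes control sides. SAP 9.7 names no sinus-level AE table for either side, so a count of uncovered sinuses would measure no missing data.

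Nor is the comparison lost. Side is recorded where available and the randomisation schedule will be listed (SAP 7), so it can be rebuilt for localised events.

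Comparing sides is also not the only route to attribution. Protocol 9.4 and 16.2.2 attribute each event to the separate devices and procedures, and SAP 9.7 presents relationship in its summaries. Disagreements between investigator and sponsor on causality go to a blinded adjudicator (Protocol 16.3).

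Some local outcomes are already assessed by side. Granulation, scarring, inflammation and edema at the frontal ostium are endoscopic efficacy grades and not AEs (Protocol 16.1). Need for intervention at Day 45 has an exact McNemar test (SAP 9.4.1).

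Two further points limit the concern. The table mockups in SAP Appendix B are not in the text available, so a by-side shell may exist. The general rule in SAP 6.1 on displays by treatment side neither names nor excludes AEs.

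All of this stands. It does not supply a stated by-side summary of bleeding, infection or pain, and the adjudicator sees only disputed events.

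**Conclusion.** The concern holds as a gap in definition and reporting. The Safety Population wording literally omits control sinuses and leaves exposure undefined. SAP 9.7 specifies only pooled totals, so the within-subject randomised comparison of localised AEs is not prespecified.

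The size is one missing summary, with no demonstrated exclusion of any event. The 10-point example shows what pooled rows can conceal under assumed counts; it does not predict a result. The primary analysis is unaffected.

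The conclusion assumes that Appendix B holds no by-side AE table. It applies only to events that can be given a side: systemic or unlocalised AEs cannot be compared between sides in this design under any definition.

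**What to change.** 1. In SAP 4.5, and to match in Protocol 4 and 18.6, define the Safety Population by subject: all subjects in whom implant placement was attempted or done, with both sinuses included. This also settles where a failed delivery belongs.
2. In SAP 9.7, add one descriptive table of sinus-localised AEs with columns for treated side, control side, both sides and not localisable, and with side-level denominators. For the most frequent terms, give the paired difference (a − b)/n with a 95% CI from a method suited to small paired counts. State in advance how the most frequent terms are chosen.
3. Add a footnote that side attribution is unblinded and recorded only where available. Showing the not-localisable column makes any incompleteness visible.

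The cost is wording in two documents and one extra table. No new data collection is needed. If Appendix B already contains such a table, only the population wording and a cross-reference in SAP 9.7 remain.
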